9.3 Secondary Efficacy Analyses

The analysis of the following list of the secondary endpoints is given below:

1. Total Pain Relief at 6 hours (TOTPAR6), 8 hours (TOTPAR8) post-dose
2. Summed Pain Intensity Difference (SPID) at 4, 6, 8, and 24 hours after first dose
3. Time to achieve a 50% reduction of baseline pain (pain at least half gone)
4. Time to onset of first perceptible pain relief (stopwatch 1)
5. Time to onset of meaningful pain relief (stopwatch 2)
6. Time to intake of first rescue medication dose
7. Subject's global evaluation of the treatment (5-point Likert Scale; 0 poor to 4 excellent) at 8 hours after the first dose of IMPs or before first intake of rescue medication (whichever was first) and at 24 hours after the first dose of IMPs

TOTPARs and SPIDs at each of their summary time points will be analyzed using the same ANCOVA model described for the primary endpoint. Note that alpha levels for secondary analyses are not adjusted for multiple comparisons.

The time to onset of event endpoints will be presented using Kaplan-Meier plots. Medians will be compared across the groups using Wilcoxon Log-rank test, and Hazard Ratios (HR) will be compared across the groups using Cox Hazard Ratio model. Time to onset will be defined as date/time from the first administration of IMPs to the date/time when the subject first reports the event (50% reduction of baseline pain, perceptible pain relief, meaningful pain relief, and intake of rescue medication – each separately). The summaries will include quartiles and HR and their corresponding 95% confidence intervals. Please see [Appendix B](#) for details on the determination of event and censoring time points.

Note that alpha levels for secondary analyses are not adjusted for multiple comparisons.

Subject's global assessment of the treatment will also be summarized with descriptive statistics (patient counts and percentages for each assessment category) at 8 and 24 hours.

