10.3 Method of assigning subjects to treatment groups (allocation)

An electronic data capture system will be used to assign a subject number at the Enrollment Visit (Visit 1). An Interactive Response Technology system (IRT, voice and web based [IVRS or IWRS]) will be used to support the drug supply chain management processes of distribution. Details of the vendor and the system will be filed in the trial master file.

The investigator or person assigned by the investigator must log into the system using their own user identification number and a password. The investigator or person assigned by the investigator will enter the subject's number and other information required by the system to obtain a medication number. The medication number is then used to select the correct package of IMPs and rescue medication to give to the subject.

Treatment allocation (randomization) will be done at the Allocation Visit (Visit 2). Subjects who comply with all inclusion criteria and do not meet any of the exclusion criteria will be randomly allocated to 1 of the 4 treatment groups in a 1:1:1:1 ratio. Treatment assignment will be performed

centrally using an IRT system prior to the first administration of IMP. Allocation will be performed using a stratified block randomization with site and, following the IMMPACT recommendations (Cooper et al. 2016), pain intensity at baseline (categories “moderate” and “severe” as defined in Section 12.2.1.1) as stratification factors.

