ADL Adorlan (tramadol HCl/diclofenac sodium); D diclofenac sodium; T tramadol hydrochloride; HCl hydrochloride. $\Delta = 1.5$ is the non inferiority margin.

The trial will be positive if at least 1 of the according 4 statistical tests rejects the according null hypothesis.

According to the Bonferroni-Holm procedure, the p-values of the 4 tests T_1 , T_2 , T_3 , and T_4 will be sorted in ascending order $p_{(1)} < p_{(2)} < p_{(3)} < p_{(4)}$ and the following algorithm will be applied to the corresponding null hypotheses $H_{(01)}$, $H_{(02)}$, $H_{(03)}$, $H_{(04)}$:

- Step 1. If $p_{(1)} < \alpha/4$ (0.625%), reject $H_{(01)}$ and move to the next step. Otherwise retain all null hypotheses and stop.
- Step 2. If $p_{(2)} < \alpha/3$ (0.833%), reject $H_{(02)}$ and move to the next step. Otherwise retain $H_{(02)}$, $H_{(03)}$ and $H_{(04)}$ and stop.
- Step 3. If $p_{(3)} < \alpha/2$ (1.25%), reject $H_{(03)}$ and move to the next step. Otherwise retain $H_{(03)}$ and $H_{(04)}$ and stop.
- Step 4. If $p_{(4)} < \alpha$ (2.5%), reject $H_{(04)}$ and move to formally testing null hypotheses related to secondary endpoints. Otherwise retain $H_{(04)}$.

The primary analysis will use an ANCOVA model with treatment, site, and baseline pain (measured on an 11-point NRS) as covariates. The pain intensity score assessed before IMP intake will be considered the baseline pain intensity and site will be used as a covariate.

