9.4 Exploratory Efficacy Analyses

The following exploratory analyses will be performed on these additional efficacy outcomes:

1. Pain Relief Score after first dose over time
2. Pain Intensity Score after the first dose over time (based on NRS)
3. Pain Intensity Difference (PID, NRS) after first dose over time
4. Peak pain relief score
5. Peak pain intensity difference
6. Time to request the first dose of rescue medication
7. Time to peak pain relief score
8. Time to peak pain intensity difference

Pain relief scores, pain intensity scores, and pain intensity difference scores over time will be analyzed at each time point using the same ANCOVA model described for the primary endpoint, TOTPAR4. Peak pain relief score and peak pain intensity difference will also be analyzed using the same ANCOVA model described for the primary endpoint.

Time to peak pain relief score and time to peak pain intensity difference be presented using Kaplan-Meier plots. Medians will be compared across the groups using Wilcoxon Log-rank test, and Hazard Ratios (HR) will be compared across the groups using Cox Hazard Ratio model. The summaries will include quartiles and HR and their corresponding 95% confidence intervals along with the p-values. Please see [Appendix B](#) for details on the determination of event and censoring time points. Note that alpha levels for exploratory analyses are not adjusted for multiple comparisons.

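### The time-to-event analyses name no baseline pain term and leave site unclear, although both factors stratify randomisation; if they are prognostic, power is lost

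*SAP*

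**What the plan says.** Protocol 10.3 sets up the allocation: "Allocation will be performed using a stratified block randomization with site and" baseline pain intensity (moderate or severe) "as defined in Section 12.2.1.1) as stratification factors". SAP 9.1 carries both factors into the primary model: "The primary analysis will use an ANCOVA model with treatment, site, and baseline pain (measured on an 11-point NRS) as covariates". SAP 9.3 and 9.4 use the same ANCOVA for TOTPAR6, TOTPAR8, SPID, the pain scores over time and the peak scores.

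For the time-to-event endpoints, SAP 9.3 gives Kaplan-Meier plots and two comparisons. The first is a test: "Medians will be compared across the groups using Wilcoxon Log-rank test". The second is a model-based estimate, which the SAP describes in these words: "Hazard Ratios (HR) will be compared across the groups using Cox Hazard Ratio model". The endpoints it names are pain at least half gone, perceptible relief, meaningful relief and rescue intake. SAP 9.4 repeats this for two exploratory endpoints: "Time to peak pain relief score and time to peak pain intensity difference be presented using Kaplan-Meier plots", followed by the same test and Cox model. Neither section names a covariate or a stratum.

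Other relevant text:
- Protocol 14.5.4 leaves these models to the SAP, so the SAP wording governs.
- SAP 8.2 confines its covariate statement to the primary model.
- SAP 8.7 says that site will be a covariate in what it calls the multivariate analysis. It does not say which analysis that is, and does not mention baseline pain.
- SAP Appendix B gives event and censoring rules only.
- SAP 11 does not explain why these endpoints are handled differently.

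**The concern.** Stratified allocation balances the arms on site and pain category more closely than simple randomisation would. A test that ignores those factors computes its variance as if the balance were down to chance. If the factors predict the outcome, that variance is too large and the test rejects too rarely. In a Cox model, leaving out prognostic factors also moves the hazard ratio from the conditional to the marginal effect, which lies closer to 1.

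Onset and rescue times are secondary evidence on how the combinations compare with the single drugs. At stake is power that the collected data could supply, and a consistent estimand: TOTPAR and SPID effects are adjusted for site and baseline pain, while the onset and rescue effects, as written, need not be.

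**Working it through.** **The plan's own figure.** The documents give no power, event count or target hazard ratio for any time-to-event endpoint. The only power figure is for TOTPAR4 (SAP 4). With 180 per arm, SD 4, margin 1.5 and one-sided alpha 0.025/4 = 0.00625, the standard error is 4 × √(2/180) = 0.422. Then 1.5/0.422 = 3.56, the critical value is 2.50, and power is Φ(1.06) = 85.5%, which agrees with the stated 85%. Allowing for 10% not evaluable, 180/0.9 = 200 per arm. This confirms the arm size used below but says nothing about the time-to-event tests, so simulation is needed.

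**Inputs from the documents.** 200 per arm, 1:1:1:1 allocation, strata of site by moderate/severe pain, 95% intervals for the hazard ratio (hence two-sided 5%), and stopwatch follow-up to 8 hours (SAP Appendix B).

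**Assumptions not in the documents.** 10 equal-sized sites on average (Protocol 14.1.1 gives 8 to 12, the SAP about 8), block size 4, exponential times with control hazard 0.25 per hour, half the subjects with NRS 5 or 6, and the strength of each factor.

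**Model.** Log hazard = log(0.25) + log(HR) × treatment − b × standardised NRS + site effect with SD s. The first set takes b = s and compares two arms, with 1000 trials at HR 1.35 and 2000 at HR 1. Unadjusted power and null rejection are for the unstratified log-rank test. Adjusted power is for Cox with treatment, site and NRS.

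| b = s | Power unadjusted | Power adjusted | Gain (points) | HR unadjusted | HR adjusted | Null rejection, unadjusted |
|---|---|---|---|---|---|---|
| 0 | 81.5% | 81.1% | −0.4 | 1.35 | 1.36 | 5.2% |
| 0.2 | 77.2% | 80.7% | 3.5 | 1.33 | 1.36 | 4.4% |
| 0.3 | 71.7% | 79.6% | 7.9 | 1.31 | 1.36 | 3.6% |
| 0.5 | 58.5% | 78.1% | 19.6 | 1.26 | 1.36 | 2.8% |
| 0.7 | 44.1% | 76.7% | 32.6 | 1.23 | 1.36 | 1.6% |

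Under the null the adjusted Cox test stays between 5.2% and 5.5%. The Monte Carlo standard error is about √(0.77 × 0.23/1000) = 1.3 points for power and √(0.05 × 0.95/2000) = 0.5 points for null rejection, so the 4.4% at SD 0.2 is not clearly below 5%.

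**Second set.** HR 1.30, with NRS entered as a slope per point, 700 trials per setting (standard error about 1.8 points).
- No prognostic effect: 69% unadjusted, 69% adjusted.
- Site SD 0.3, slope −0.1: 61% against 68%, HR 1.27 against 1.30. A repeat with hazard 0.27 per hour and 8-hour censoring gave 62% unadjusted, 67% with site only and 68% with both.
- Site SD 0.5, slope −0.15: 54% against 67%, HR 1.25 against 1.31. The repeat gave 56%, 68% and 70%. Null rejection of the unstratified log-rank was 3.7%.
- Site SD 0.1, slope −0.1 (repeat only): 71% against 73%.

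**Reading across.** At moderate strength the gains are 68 − 62 = 6, 68 − 61 = 7 and 7.9 points. At about SD 0.5 they run from 68 − 56 = 12 (site only), through 67 − 54 = 13 and 70 − 56 = 14, to 19.6. Where the two terms were separated, site supplied 67 − 62 = 5 of 6 points and 12 of 14. That split depends on the relative strengths assumed.

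**Full stratification.** A log-rank test stratified by site and pain category has about 10 × 2 = 20 strata. With no prognostic effect its power is 76.4% against 81.5% unstratified. At SD 0.5 it is 72.2%, better than 58.5% unstratified but below 78.1% for the adjusted Cox model.

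**The case against.** The strongest reply is that SAP 8.7 may already put site in the Cox model. The Cox model is a natural reading of its multivariate analysis, and in the runs that separated the terms, adding baseline NRS to a site-adjusted model gained only 1 to 2 points, within simulation error. This stands as far as it goes: a flat statement that site is ignored is not supported. But the sentence does not name the Cox model, cannot apply to a log-rank test and does not cover baseline pain.

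Secondly, strong prognostic effects may be implausible. A site SD of 0.5 means that sites one SD above and below the mean differ by exp(1.0) = 2.7-fold in hazard; at 0.7 it is exp(1.4) = 4.1-fold. Surgery and anaesthesia are standardised, all sites are in Mexico, and baseline NRS is limited to 5 to 10. That argues for the lower rows of strength, where the loss is small.

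Thirdly, a reader might infer that the unadjusted hazard ratios are biased. They are not. The hazard ratio is non-collapsible, so the unadjusted value estimates a marginal effect, and neither version moves when the true ratio is 1. The conservative test and the lost power remain whichever ratio is preferred.

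Finally, a reader might assume that time to rescue request gets the same unadjusted test. The methods text of SAP 9.3 and 9.4 does not include it. Only a censoring rule and table and figure titles exist, so its method is unstated.

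**Conclusion.** The point holds in limited form. Baseline pain is specified for none of the six time-to-event comparisons that have a stated method, site is unclear for the Cox models, and no strata are given for the log-rank test. If the two factors are prognostic, the unadjusted tests are conservative. The power loss is about 0 points with no effect, about 4 at log-hazard SD 0.2, 6 to 8 at moderate strength and 12 to 20 at about SD 0.5. Null rejection falls from 5% to about 4.4% at SD 0.2 and to 2.8–3.7% at about SD 0.5. All of this rests on assumed prognostic strengths, because the documents give none.

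The documents do not support reading this as a threat to the trial's conclusion. Success depends on the four TOTPAR4 tests, whose ANCOVA contains both factors. The affected endpoints are secondary or exploratory and are tested without multiplicity adjustment. The error runs against finding a difference and does not raise the false-positive rate. Severity is minor.

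**What to change.** In SAP 9.3 and 9.4, specify Cox models with treatment, site and baseline NRS, the same terms as the ANCOVA. Take the treatment p-value and hazard ratio from that model, and state that the site sentence in SAP 8.7 applies to it. If a log-rank test is also shown, label it supportive and stratify it by baseline pain category only. Adding site gives up to about 20 strata and can cost power, while leaving site out means that this display stays conservative with respect to site. State a method for time to rescue request as well.

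The cost is SAP wording and one model statement, with no new data. The simulations show essentially no power loss from the adjusted Cox model when neither factor matters (81.1% against 81.5%, and 69% against 69%). The one change in meaning is that the reported hazard ratio becomes conditional on site and baseline pain, and the SAP should say so.

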1.2 Trial objectives and endpoints/outcomes

Objective	Endpoint/outcome

Primary
 
The primary objective is to demonstrate the analgesic efficacy of the tramadol HCl/diclofenac sodium FDC at 2 dose levels (50 mg/50 mg, 25 mg/25 mg) in comparison to the monotherapy of diclofenac sodium 50 mg and tramadol HCl 50 mg.
 
The specific primary objective is to demonstrate that:
 
 • Either tramadol HCl/diclofenac sodium 50 mg/50 mg has superior analgesic efficacy than monotherapy with diclofenac sodium 50 mg, • Or tramadol HCl/diclofenac sodium 50 mg/50 mg has superior analgesic efficacy than monotherapy with tramadol HCl 50 mg, • Or tramadol HCl/diclofenac sodium 25 mg/25 mg is not inferior to monotherapy with tramadol HCl 50 mg, • Or tramadol HCl/diclofenac sodium 25 mg/25 mg is not inferior to monotherapy with diclofenac sodium 50 mg. 	
Primary
 
 • Pain relief expressed as Total Pain Relief over the 4 hours post-dose period (TOTPAR4).

Secondary
 
To further explore the efficacy of the tramadol HCl/diclofenac sodium FDC at 2 dose levels (50 mg/50 mg, 25 mg/25 mg) in comparison to the monotherapy of diclofenac sodium 50 mg and tramadol HCl 50 mg.
	
Secondary
 
 • Total Pain Relief at 6 hours (TOTPAR6), 8 hours post-dose (TOTPAR8). • Summed Pain Intensity Difference (SPID) at 4, 6, 8, and 24 hours post-dose. • Time to achieve a 50% reduction in baseline pain (pain at least half gone). • Time to onset of first perceptible pain relief. • Time to onset of meaningful pain relief. • Time to intake of first rescue medication dose.

Grünenthal
Confidential

Protocol KF8001-01
including Amendment 02

Page 4 of 72
DMS version 3.0
19 Oct 2017

Objective	Endpoint/outcome
To compare the overall impression of the subject on the treatment they received.	
 Subject's global evaluation of the treatment (5-point Likert Scale) 8 hours or before first intake of rescue medication (whatever the first) and 24 hours after the first dose of IMPs.
To evaluate the safety profile of the FDC product in comparison to the safety profiles of the monotherapies.	
 Incidence and type of adverse events.

Data collected not directly supporting an objective

Data collected	Rationale for collecting data not directly supporting an objective

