12.2.3 Subject's global evaluation of the treatment (Likert scale)

The subject's overall impression (overall assessment) of the analgesic efficacy of the IMPs will be obtained 8 hours after the first dose of IMPs or before first intake of rescue medication (whatever the first) and 24 hours after the first dose of IMPs. Subjects will be asked the following question and will be requested to also record the time at which it was answered:

“How would you rate the study medication you received for pain?”

- Excellent (4)
- Very good (3)

- Good (2)
- Fair (1)
- Poor (0)

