14.5.4 Analysis of additional efficacy outcomes

The pain intensity scores (NRS) at all the time points (see Section 1.8) after the first dose of IMPs will be analyzed by an ANCOVA model with treatment, site, and baseline pain as covariates.

Pain relief expressed as Total Pain Relief after 6 hours and after 8 hours (TOTPAR6, TOTPAR8) will be analyzed with the same ANCOVA model and missing data handling as the primary analysis.

The specification of the statistical analysis of the following additional efficacy outcomes including statistical analysis models, formal statistical tests, and further specifications in detail will be provided in the statistical analysis plan:

- Pain intensity score reductions (Pain Intensity Difference [PID], NRS) for each time point after the first dose of IMPs.
- Summed Pain Intensity Difference (SPID) at 4, 6, 8, and 24 hours after the first dose of IMPs.
- Pain relief scores for each time point after the first dose of IMPs.

-
- Time to onset of first perceptible pain relief (Stopwatch 1).
 - Time to onset of meaningful pain relief (Stopwatch 2).
 - Time to achieve a 50% reduction in baseline pain (pain at least half gone).
 - Time to request the first dose of rescue medication.
 - Time to first intake of rescue medication.
 - Subject's global evaluation of the treatment (5-point Likert scale) 8 hours or before first intake of rescue medication (whatever the first) and 24 hours after the first dose of IMPs.

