8.3 Handling of Dropouts or Missing Data

Diligent attempts will be made to limit the amount of missing data in the pain relief assessments used to determine the primary efficacy endpoint. Efforts will be made to encourage but not to enforce subjects to not start rescue medication intake if not needed. Assessments with missing date/time of evaluation will be considered unreliable and removed from all analyses and treated as missing values. Assessments made after the subject's first dose of rescue medication will be considered missing values and excluded from the analyses. Other than the methods outlined below for TOTPAR4, TOTPAR6, and TOTPAR8, no imputations will be performed to replace missing values for any of the other endpoints; those missing values will be left as missing.

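### The SAP specifies no between-group analysis for the global evaluation, and SAP 8.3 as worded would drop 24-hour ratings given after a first rescue dose

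*SAP*

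**What the plan says.** **Objective.** Protocol 1.2 states the secondary objective as "To compare the overall impression of the subject on the treatment they received". SAP 2 repeats it. The five-category global evaluation is its only endpoint.

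**What the protocol leaves to the SAP.** Protocol 14.5.4 lists the global evaluation among the outcomes for which "statistical analysis models, formal statistical tests, and further specifications in detail will be provided in the statistical analysis plan".

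**What the SAP provides.** SAP 9.3 assigns the primary ANCOVA model to TOTPAR and SPID, and a rank-type test with a Cox model to the time-to-event endpoints. For the global evaluation it says only that the subject's "global assessment of the treatment will also be summarized with descriptive statistics", namely counts and percentages per category at 8 and 24 hours. Appendix C plans one FAS table for it (14.2.9.1).

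**When the ratings are taken.** Protocol 12.2.3 schedules them at 8 hours "or before first intake of rescue medication (whatever the first) and 24 hours after the first dose of IMPs". The first rating is therefore brought forward if rescue is needed. The 24-hour rating has no such provision.

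**Rescue and missing data.** Under SAP 8.3, assessments made after the "first dose of rescue medication will be considered missing values and excluded from the analyses". Outside TOTPAR4, TOTPAR6 and TOTPAR8, "no imputations will be performed to replace missing values for any of the other endpoints".

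**The concern.** There are two separate gaps.

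First, an objective worded as a comparison ends in a tabulation. No effect measure, interval, model or test is specified, although the protocol said that the SAP would supply them. Any between-arm statement in the report would then rest on reading percentages by eye or on an analysis chosen after unblinding.

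Second, subjects rescued before the 24-hour rating are asked to complete all procedures (Protocol 10.5), so their ratings should be collected. SAP 8.3 read literally then removes them. Protocol 10.5 describes rescue as available when trial medication does not relieve pain sufficiently. Removal therefore depends on the very thing that the rating measures, and a less effective arm would be expected to lose more of its low ratings. The table would still carry the FAS label.

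**Working it through.** **1. Is a comparison specified anywhere?**

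| Place | Treatment of the global evaluation |
|---|---|
| Protocol 1.2, SAP 2 | objective is to compare |
| Protocol 14.5.4 | models and formal tests deferred to the SAP |
| SAP 9.3 | counts and percentages per category |
| SAP 9.4 | not covered, although the added exploratory peak scores get ANCOVA |
| SAP Appendix C | one table, 14.2.9.1 |
| SAP 11 | no change reported, although moving dental history to a listing is reported |

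SAP 9.3 says that the rating is *also* summarised, but no other analysis of it appears.

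**2. Does the post-rescue rule reach the 24-hour rating?** The SAP 8.3 exclusion is worded for assessments in general, and the no-imputation sentence covers all endpoints other than the TOTPARs. SAP 9.3, Appendix A item 8 and Appendix B contain no exemption. SAP 5.1 bases by-visit percentages on available data, with missing values generally out of the denominator. Read literally, a 24-hour rating that follows a first rescue dose leaves the table. A first rating taken before rescue stays.

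**3. How many ratings?** The plan's only power figure concerns TOTPAR4. It reproduces (85.5% by the normal approximation and 85.2% by the noncentral t, for 180 per arm, difference 1.5, SD 4, one-sided 0.00625) and is not at issue. No rescue rate is given, so it is an assumption here. With 200 allocated per arm and a fraction r rescued before the rating, at most 200 × (1 − r) ratings remain: 180, 140, 100 and 60 for r = 10%, 30%, 50% and 70%.

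**4. What does selection do to the difference?** All inputs in this step are assumptions.

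- The latent satisfaction score is normal with SD 1, mean 0 in the weaker arm and 0.5 in the stronger.
- It is cut at −1.0, −0.3, 0.4 and 1.2 to give categories 0 to 4.
- A second score with the same arm mean, correlated 0.5 or 0.8 with the first within arm, triggers rescue when it falls at or below a threshold.
- Rescue does not itself change the rating.

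The mean rating with nobody excluded is the sum of P(score > cut) over the four cuts:

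- weaker arm: 0.841 + 0.618 + 0.345 + 0.115 = 1.92
- stronger arm: 0.933 + 0.788 + 0.540 + 0.242 = 2.50
- difference: about 0.58; the simulation runs gave 0.58 to 0.59.

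Simulated with one million subjects per arm:

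| Rescue threshold | Rescued, weaker vs stronger | Difference, nobody excluded | Difference, non-rescued only (correlation 0.5; 0.8) |
|---|---|---|---|
| −1 | 16% vs 7% | 0.59 | 0.50; 0.45 |
| −0.5 | 31% vs 16% | 0.58 | 0.45; 0.37 |
| 0 | 50% vs 31% | 0.58–0.59 | 0.40; 0.29 |
| 0.5 | 69% vs 50% | 0.59 | 0.36; 0.21 |

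The mean among the kept ratings is also higher in both arms. At threshold 0 and correlation 0.8 it is 2.72 and 3.00, against 1.92 and about 2.5 with nobody excluded.

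**The case against.** **The exclusion may not be meant for this endpoint.** SAP 8.3 opens on missing pain relief assessments. SAP 8.3.2, 9.2.1 and 11 explain the exclusion by the drop in pain after rescue. Where the SAP limits another endpoint to pre-rescue data (the peak scores, several of the time-to-event rules), it says so in that endpoint's own definition, and Appendix A item 8 has no such limit. This stands as an argument about intent. It does not settle the text, because the exclusion is general and the next sentence speaks of all other endpoints. A programmer following SAP 8.3 would apply it.

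**The first rating is a safeguard.** A subject rescued within 8 hours still contributes a pre-rescue rating, and differential rescue is analysed directly as time to first intake. Both points are correct. A reader might infer that rescued subjects disappear from the endpoint altogether; they do not. Nor is every rescued subject affected, only those whose first rescue dose comes before the 24-hour rating.

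**The difference need not vanish.** A reader might construct a case in which the arms look identical at 24 hours. That requires ratings to be equal across arms among the rescued and among the non-rescued, which nothing in the documents supports. The runs above show shrinkage, not disappearance. The planned table also shows counts, so unequal numbers would be visible.

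**Comparison need not mean a test.** Tables are by treatment group, and the safety objective is also comparative yet is analysed descriptively. This has some force, and it would be wrong to say that the arms are not compared at all. But for this endpoint Protocol 14.5.4 promises models and formal tests.

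**Ratings after rescue mix in the rescue drug.** True. The question asks about the study medication, and which quantity to estimate at 24 hours is partly a matter of choice. The SAP should state its choice.

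**Conclusion.** Both gaps stand. The missing between-group analysis is a plain mismatch between the protocol's commitment and the SAP, not recorded in SAP 11. The loss of post-rescue 24-hour ratings follows from the literal wording of SAP 8.3 and may be unintended.

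The expected consequence is attenuation. In the assumed scenarios the non-rescued difference keeps about 76% to 85% of its size at the lowest rescue rates (0.45/0.59 and 0.50/0.59) and about 36% to 61% at the highest (0.21/0.59 and 0.36/0.59). These figures rest on an assumed 0.5 SD shift, assumed cut points and correlations, and a common rescue threshold in both arms. They also assume that rescue leaves the rating unchanged. If rescue raises ratings, the difference among all recorded ratings would be smaller than 0.59 too.

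A reader might infer that the trial's main result is in doubt. It is not: this is one secondary endpoint, SAP 9.3 leaves it unadjusted for multiplicity, and the four TOTPAR4 tests do not use it. The change should still be made before unblinding.

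**What to change.** 1. In SAP 8.3, state that the 24-hour global evaluation is exempt from the post-rescue exclusion, so that all recorded ratings count. Note beside it that these ratings then include any effect of rescue medication.
2. In SAP 9.3, add a proportional-odds model with treatment, site and baseline pain at each of the two time points (8 hours or before first rescue; 24 hours). Report odds ratios with 95% confidence intervals for the four planned contrasts.
3. Give nominal p-values for the two 50 mg/50 mg superiority contrasts only. For the two 25 mg/25 mg contrasts, report estimates and intervals, because no non-inferiority margin exists on this scale and a p-value would have no defined null hypothesis.

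If the sponsor prefers a purely descriptive analysis, the objective should be reworded and SAP 11 should record the departure from Protocol 14.5.4. The first change is needed in either case.

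The cost is a few sentences in the SAP, one standard model and its output. No new data are needed. The price in interpretation is that the 24-hour rating then describes the trial treatment together with any rescue taken.
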